## 6. DATA COLLECTION

### 6.1 Methods

The data will be collected on to a web-based system designed and coordinated by the Trial Manager and Data Administrator at Royal Papworth Hospital. They will be responsible for training researchers to use the system and will conduct initiation visits.

QoL will be measured using the SF-12 and EQ-5D-3L at:

- baseline
- on hospital discharge
- at 1 month
- and every month for 12 months

Previous work has shown that, as a general rule, routine patients undergoing a routine cardiac operation are likely to have made a full recovery within 3 months if there are no complications and within 6 months if there are complications. To allow additional time for a return to preoperative QoL level, exceed it and achieve QoL benefits that reverse any QoL loss from surgery, QoL assessment will continue up to 12 months postoperatively, at which time patients who have not regained baseline QoL are unlikely to demonstrate any further significant QoL benefit.

### 6.2 Baseline & Discharge data collection

The Researcher at each centre will enter the baseline and discharge data directly on to the OpenClinica database or alternatively enter the data on to a printed form until such time as it can be entered directly.

The baseline QoL questionnaires should be completed independently by the patient this can be completed either electronically if the recruiting site can support this or on paper based and entered manually by the researcher onsite.

Data collected at baseline will include overall risk stratification, EuroSCORE II which already records data on a number of factors and co-morbidities known to be associated with QoL: age, sex, cardiac disease and complexity, cardiac function, diabetes, neurological and musculoskeletal function, respiratory function and

renal function. To this, we shall add factors not included in EuroSCORE II but known to be correlated with QoL, patient outlook (objectively assessed by the *Life Orientation Test* and the *Positive and Negative Affect Scale*), socio-demographic status and assessment of frailty . Frailty will be assessed by the Essential Frailty Toolset by Afilalo (a4 item scale encompassing lower extremity weakness, cognitive impairment, anemia and hypoalbuminemia.)

### 6.3 Follow up questionnaires

After the discharge information is provided by the recruiting hospital the follow up of patients will return to the central Papworth team. Patients will be asked to complete the QoL questionnaires monthly. Patients will be able to use their own devices to enter QoL data directly into an electronic system, allowing for collection of high-quality, timely data in a convenient way. Patients will be notified when they are due to complete a questionnaire by email or text message; an underlying audit trail will provide evidence that the participants completed the forms in the timeframe dictated by the protocol

Patients who are not able to enter their data electronically will be provided with paper questionnaires, which will be scanned directly into an electronic database. This will forgo the need for any manual data entry, therefore reducing significantly reducing cost and errors.

## 7. MANAGEMENT & GOVERNANCE

The Clinical Project Manager (CPM) and the Trial Manager (TM) (who are based at Royal Papworth) will work directly with the other centres to coordinate all aspects of the study and ensure that the study is conducted according to ICH-GCP standards. They will be responsible for any necessary training.

### 7.1 Sponsorship

Royal Papworth Hospital NHS Foundation trust has assumed the responsibility of Sponsor. The respective responsibilities of the sponsor, investigator and Trial Manager will be identified and delegated at the start of the study.

### 7.2 Study project team

The study project team will include the chief investigator, statisticians, data manager, trial manager, project manager. This group will provide daily oversight of the initiation and subsequent progress of the trial. Meetings will be at Papworth and will be frequent (monthly) during the start-up and early recruitment phases and less frequent (3-6 monthly) subsequently. E mail or teleconferencing will be used for input from collaborators at other centres.

### 7.3 Trial Steering Committee

A Trial Steering Committee (TSC), consisting of at least two independent members, a patient representative and the Chief Investigator will be convened and meet once a year. This committee will monitor the progress of the trial in relation to the stated milestones and the interim and overall objectives and instigate any remedial actions

### 7.4 Monitoring and Audit

Recruitment of patients and collection of data will be monitored by the Papworth Trial manager on a regular basis.

The recruitment process will be monitored from 6 months since the study commences, this is when we expect centres to be fully functioning and contributing to recruitment. The first interim monitoring is based on the predictive model proposed by Anisimov and the successive recruitment will be evaluated regularly and reported in data monitoring committee and trial steering committee. If the recruited number is below the expected lower boundary, incentive measures will be discussed and implemented after and a TSC meeting will be call upon to discuss this.

## 8. ETHICAL AND REGULATORY CONSIDERATIONS

Before the start of the study, a favourable opinion will be sought from a REC & HRA for the study protocol, informed consent forms and other relevant documents.

Before any site can enrol patients into the study, the Chief Investigator/Principal Investigator or designee will ensure that appropriate approvals from participating organisations are in place and an initiation has been conducted.

All patients will be given sufficient time to consider and discuss the study the investigator will ask them to provide written consent. As part of the trial design patients will be asked to provide consent for their name, contact phone number and email to Royal Papworth Hospital. This will be fully explained in the patient information sheet and consent form.

### 8.1 AMENDMENTS

*All substantial amendments must be approved the REC and the individual Trusts (via their R&D departments) before being implemented in the individual centres.*

For any amendment to the study, the Chief Investigator or designee, in agreement with the sponsor will submit information to the appropriate body in order for them to issue approval for the amendment. The Chief Investigator or designee will work with sites (R&D departments at NHS sites as well as the study delivery team) so they can put the necessary arrangements in place to implement the amendment to confirm their support for the study.

## 9. DATA PROTECTION AND PATIENT CONFIDENTIALITY

All investigators and study site staff must comply with the requirements of the Data Protection Act 2018 with regards to the collection, storage, processing and disclosure of personal information and will uphold the Act's core principles.

With patient consent personal information will be collected and provided to Papworth Hospital. This information will be transferred securely through Openclinica our electronic data capture system. The patient identifiable information will be coded and access will only be granted to the individual staff members completing the study follow ups. Data will be collected using the Enterprise version of OpenClinica, the system is fully validated and GCP + CFR21 compliant. OpenClinica Optimized Hosting has numerous features to ensure the security and privacy of data. All data transfer between the OpenClinica system and users is encrypted using SSL/TLS. Access to OpenClinica within the Trust is controlled by the Data Management lead. Each user has their own account to access OpenClinica which requires a strong password. A robust audit trail within OpenClinica tracks all changes to the data and retains a history for each variable, including old and new value, date and time of the change and who made it.

All data used in the formulation of reports to investigators, the sponsor, funder or ethics will only contain anonymised data. The Data Management lead will ensure confidentiality of data is preserved when the data is transmitted to sponsors and co-investigators.

Patient identifiable information will be stored until the end of the study at 3 years; the data will remain stored for 15 years as per the Trust policy. The study data will be exported from OpenClinica and archived locally on Papworth servers. [name] will act as custodian for the data.

## 10. FINANCE & INSURANCE

This study is funded by the J.P. Moulton Charitable Foundation. Clinical Trial Agreements will be agreed with all participating sites. Normal NHS indemnity will provide indemnity and/or compensation for negligent harm. NHS Indemnity does not offer no-fault compensation i.e. for non-negligent harm. However the normal National Health Service complaints mechanisms will still be available to participants.

The study team will be applying for the Clinical Research Network portfolio adoption for this study. If accepted, sites are able to apply for service support costs for screening and consent time.

## 11. PATIENT & PUBLIC INVOLVEMENT

Patients and the public are represented by lay members of the Trial Steering Committee. Both the electronic and paper versions of data collection are currently being tested by our patient research ambassadors who will help refine the method to ensure it is user-friendly.

As a preliminary exploration, we approached a series of patients attending cardiac surgical clinics to consider surgery for their cardiac condition. They were shown the TUTE calculator (which predicts their likely benefit in terms of survival) and were asked if they would consider a similar tool predicting QoL outcomes useful to them. The response was invariably positive.

Throughout the course of the study we shall hold yearly patient events to discuss the construction of the QoL prediction tool and in particular the way patients would want this information presented to them so it will be understandable and of value. During the patient events we shall also ask previous cardiac patients what information they would have found useful in aiding them to make the decision to undergo surgery. This development will help design the end product that would be made available to patients and doctors.

Once data collection is completed, a descriptive report will outline the pattern of QoL loss and gain over time after cardiac surgery. The data will then be analysed by logistic regression to identify the factors predictive of loss and gain in QoL outcomes. A full analysis of factor interactions will be carried out. The data will be divided into a development dataset and a validation dataset. The development dataset will then be used to construct a number of risk models to predict the extent and likelihood of any QoL benefit or loss from cardiac surgery. All the models will then be tested for calibration and discrimination against the validation dataset to identify the most useful and robust model. The chosen model will then be developed into a QoL outcome calculator (QoLculator) which will be offered for testing and external validation, following which the calculator will be made available on-line and as a mobile phone app for patients and doctors.

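### Section 11 describes factor and interaction selection before the development/validation split, so it reads as selection on all patients; the text should confine selection to the development dataset

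*Protocol*

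**What the plan says.** The last paragraph of protocol section 11 (Patient & Public Involvement) sets out how the calculator will be built. In the order of the text:

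1. After a descriptive report: "The data will then be analysed by logistic regression to identify the factors predictive of loss and gain in QoL outcomes".
2. "A full analysis of factor interactions will be carried out".
3. "The data will be divided into a development dataset and a validation dataset".
4. "The development dataset will then be used to construct a number of risk models".
5. "All the models will then be tested for calibration and discrimination against the validation dataset to identify the most useful and robust model".
6. The chosen model becomes a calculator, "which will be offered for testing and external validation, following which the calculator will be made available on-line".

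The candidate factors are in section 6.2. From EuroSCORE II come "age, sex, cardiac disease and complexity, cardiac function, diabetes, neurological and musculoskeletal function, respiratory function and" renal function. The protocol then says "To this, we shall add factors not included in EuroSCORE II but known to be correlated with QoL, patient outlook", and names the Life Orientation Test, the Positive and Negative Affect Scale, socio-demographic status and frailty.

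Section 5.5 names the risk model (logistic or multilevel logistic regression on the third primary outcome). It does not mention interactions or the split.

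**The concern.** A validation set gives an honest check only if its patients took no part in choosing the model. Step 1 is carried out on the data, the same object that step 3 later divides, and step 2 follows without naming any other dataset. Read in sequence, the validation patients help to decide which factors and interactions are carried forward.

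Refitting the coefficients in the development dataset afterwards does not undo this. A chance interaction picked on all patients was picked partly because it happened to appear in the validation patients too, so it will tend to look good there. Step 5 then uses that validation set to choose the final model.

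The product is a calculator meant to inform individual consent. At stake is a model that looks better than a simpler one internally but predicts slightly worse, with exaggerated differences between patients, when used on others.

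**Working it through.** **The plan's own figure.** Section 5.1 gives a minimum of 6670 patients for a sensitivity of 0.75 ± 0.03 at 95% confidence with 12% events. Events needed: 1.96² × 0.75 × 0.25 / 0.03² = 800.3. Patients: 800.3 / 0.12 = 6669.2, so 6670 is reproduced. It is used below as the size of the analysed dataset.

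**Assumed inputs.** The protocol does not give these:
- *Factors:* 14, counted from section 6.2 (nine from the EuroSCORE II list, one Life Orientation score, two affect scores, socio-demographic status, frailty). Plausible range 8 to 20.
- *Interactions examined:* all two-way pairs, C(14,2) = 91.
- *Screening level:* 5%, with 1% as sensitivity.
- *Split:* 50:50 to 80:20.
- *Event rate:* about 12%. Section 5.1 gives this for not regaining QoL; the rate for the modelled outcome, net benefit, is not stated.
- *True interactions:* none, which is the worst case.

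**Expected chance interactions.** At 5%: 91 × 0.05 = 4.55. With 8 factors, 28 × 0.05 = 1.4; with 20 factors, 190 × 0.05 = 9.5. At 1% with 14 factors: 91 × 0.01 = 0.91.

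**One null interaction.** Let f be the development fraction. Then z(all) = √f · z(dev) + √(1−f) · z(val). Given selection at |z(all)| > 1.96, the mean of |z(all)| is 2 × 0.05845 / 0.05 = 2.338, so the mean z in the validation set, in the selected direction, is √(1−f) × 2.338. The percentages come from 4 million draws.

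| Term selected on | Split | Mean z in validation | Same sign in both parts | p<0.05 in validation, same direction |
|---|---|---|---|---|
| All patients | 50:50 | 1.65 | 97% | 33% |
| All patients | 2:1 | 1.35 | 95% | 23% |
| All patients | 80:20 | 1.05 | 88% | 16% |
| Development only | any | 0 | 50% | 2.5% |

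**Whole models, which is what step 5 compares.** Simulation with 6670 patients, seven normal and seven binary predictors (log-odds 0.25–0.30 each), 11.9% events and 150 replicates per split. Each interaction was screened at 5% on all patients. The model was refitted in the development part, then evaluated in the validation part and in 20,000 new patients. About 4.3 false interactions were kept.

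| Split | Validation AUC, false terms v main effects | New-patient AUC, false terms v main effects |
|---|---|---|
| 50:50 | 0.689 v 0.686 | 0.681 v 0.687 |
| 2:1 | 0.694 v 0.690 | 0.684 v 0.689 |

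The AUC loss in new patients is 0.687 − 0.681 = 0.006 and 0.689 − 0.684 = 0.005. At 50:50 the calibration slope in new patients falls from 0.93 to 0.86, while validation shows 0.91.

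How often the model with false interactions beat main effects (5% screen):

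| Run | Screen on all patients: wins validation | Screen on all patients: wins in new patients | Screen on development only: wins validation |
|---|---|---|---|
| About 11.5% events | 83–85% | 1–3% | 2–7% |
| About 10.4% events | 79–85% | 1% or less | 4–13% |

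**Sensitivity to the threshold.** At 1%, the chance that at least one false term is kept is 1 − 0.99^91 = 0.60. When one was kept, the false model won validation in 85–91% of replicates, so overall 0.60 × 0.85 to 0.60 × 0.91 = 51–55%. That agrees with about half seen directly. New-patient AUC was 0.692 v 0.694, a loss of 0.002.

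**The case against.** The strongest reply is that the protocol does not state a leak. The interaction sentence names no dataset, and neither it nor the split sentence carries the time word that links the other steps. The one sentence that assigns data to modelling is explicit: models are built on the development dataset, and choosing terms is part of building a model. The paragraph is a narrative in the public-involvement section rather than in section 5.5. The interaction analysis might also be purely explanatory, since section 5.5 separates inferential testing from the risk model. This much stands: selection on all patients is what the order suggests, not something the protocol proves. It does not remove the need for clarification, because the factor-identification step is placed on the data before they are divided, and building on the development dataset is compatible with terms already chosen on everyone.

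A reader might infer three stronger things that the protocol does not support.

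- *That missing multiplicity control is itself a fault.* Thresholds and selection rules for interactions are commonly left to the statistical analysis plan, which is not at hand. For a prediction model, overfitting matters more than familywise error.
- *That several chance interactions are to be expected in the calculator.* This depends on an unstated threshold and number of factors, and nothing says that every significant interaction enters the model.
- *That validation could not reveal chance interactions.* Even after selection on all patients, about 67–84% of null terms would not reach p<0.05 in the validation set, and an external validation is planned before release. That step comes after the model has been chosen, however: it could show poor performance but would not correct the internal choice.

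**Conclusion.** The point holds as an ambiguity that should be settled, with the more natural reading being the harmful one. If factors and interactions are selected on all patients, the validation comparison is optimistic and will usually favour a model carrying chance interactions over the better simple one.

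The direction of the bias does not depend on the assumed inputs; its size does. Under a 5% screen, 14 factors and no true interactions, the internal check picks the wrong model in roughly four replicates out of five, against a small minority when screening is confined to the development part. The resulting loss of discrimination is modest, the calibration loss is more noticeable, and both shrink with a stricter screen. This is a cheap improvement to the integrity of the internal validation. It is not evidence that the calculator would fail.

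**What to change.** In section 11, move the sentence on dividing the data ahead of the sentence on identifying predictive factors, and add: *All selection of factors and interactions will use the development dataset only, or will be repeated inside each resample where resampling is used.*

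This is a wording change and needs no new data. The downside is fewer patients for term selection. At 12% events, 6670 × 0.12 × 2/3 ≈ 534 events would be available under a 2:1 split and 6670 × 0.12 × 1/2 ≈ 400 under a 50:50 split, against about 800 in all. Repeating selection inside resamples of the full dataset avoids most of that loss.

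A pre-named short list of interactions, or a joint test as a gate, is a modelling preference and is not needed to close this gap.

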## 5. RECRUITMENT AND SAMPLING

### 5.1 Sampling

The study will recruit a total of 8004 patients over two years and follow them up for 12 months. This sample size was derived as follows: according to Abah et al the percentage of people expected not to regain QoL after heart surgery and after 12 months is between 8-19%. Additionally, there is a 4% predicted mortality rate for heart surgery in the UK in the higher risk population which is the subject of this study. Therefore, a conservative estimate is that 12% of patients in this study would not regain QoL. Assuming the 12% rate as a reference value, with a minimum of 6670 patients we would be powered to produce a predictor tool with a sensitivity of at least 0.75 (or true positive rate to identify those patients that do not regain QoL after surgery) and a 3% error ( $0.75 \pm 0.03$ ) at the 95% confidence level. Anticipating a non-response rate of 20%, we will recruit an additional 1334 patients to compensate for this, giving a total of 8004. Based on the above, the study will estimate the proportion of patients who do not regain QoL after 12 months with a 95% confidence of  $\pm 0.7\%$  (for a rate of 8%) and  $\pm 0.8\%$  (for a rate of 12%) with 6670 patients.

Recruitment and drop-out rates will be continuously monitored by the trial steering committee (TSC). To recruit 8004 patients, we plan to approach all 36 cardiac centres in the UK. Assuming only 30 centres take part (a feasible number based on our NIHR ETTAA study) and a two-year recruitment period, there will be 20000 patients with a EuroSCORE II  $\geq 3$  who would be eligible for the study over two years. Our sample size calculation requires that 40% of the eligible patients consent over the two-year period. This translates into no more than 134 patients per centre per year, a recruitment target that is conservatively achievable. Based on our original approach to 5 centres, the recruitment rate will average 192 patients per centre per year, so that the required 134 patients per centre per year is achievable and will be carefully monitored by the project management team and the TSC as described in the section 9.4 of this protocol.

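### The ±0.03 precision for sensitivity uses all 6670 patients, but the models are tested in a validation part only, and that part also chooses the model

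*Protocol*

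**What the plan says.** Protocol section 5.1 (Sampling) sets the sample size by the precision of a sensitivity estimate. It begins "Assuming the 12% rate as a reference value" and continues "with a minimum of 6670 patients we would be powered to produce a predictor tool with a sensitivity of at least 0.75", with an error of 3 percentage points "at the 95% confidence level". The total is then raised to 8004 for 20% non-response. Nothing in the calculation allows for holding part of the data back.

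The last paragraph of section 11 (Patient & Public Involvement) describes how the risk model will be built: "The data will be divided into a development dataset and a validation dataset". Next, "The development dataset will then be used to construct a number of risk models". All of these are then to be "tested for calibration and discrimination against the validation dataset to identify the most useful and robust model". The chosen model becomes the calculator, which is to undergo external validation before release. No split ratio, number of models or external dataset is given.

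Section 5.5 (Statistical analysis) does not mention a split. It places the risk model on the third primary outcome, positive net QoL benefit.

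**The concern.** Two statements in the protocol do not fit together. Section 5.1 spends every expected case on the sensitivity estimate. Section 11 tests the models on only a part of those cases. If sensitivity comes from the validation part, it is less precise than stated. If it comes from all 6670 patients, it includes the data on which the model was fitted and is apparent rather than validated performance.

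The validation part also has a second job, which is to decide which model wins. The best of several models on one dataset is partly the luckiest on that dataset, so its performance there overstates what it will do elsewhere.

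The calculator is the study's main product and is meant to inform patients deciding on surgery. Its performance is the stated basis for recruiting 8004 people.

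**Working it through.** **Inputs.** From section 5.1: sensitivity 0.75, half-width 0.03, 95% confidence (z = 1.96), case rate 12%, N = 6670. Assumed, because section 11 gives no ratio: validation share f of 50%, one third, 30% or 20%.

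**Step 1: reproduce the protocol's figure.**
Cases needed = 1.96² × 0.75 × 0.25 / 0.03² = 800.3.
Patients needed = 800.3 / 0.12 = 6669.4, which matches 6670. All 6670 patients give 0.12 × 6670 = 800 cases and a half-width of 0.030. There is no slack.

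**Step 2: half-width in the validation part.**
Half-width = 1.96 × √(0.75 × 0.25 / (rate × 6670 × f)).

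The second rate, 23%, is the top of section 5.1's own range: 19% not regaining QoL plus 4% mortality. The 12% is the bottom: 8% + 4%.

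| Validation share | Patients | Cases at 12% | Half-width at 12% | Half-width at 23% |
|---|---|---|---|---|
| all | 6670 | 800 | ±0.030 | ±0.022 |
| 50% | 3335 | 400 | ±0.042 | ±0.031 |
| one third | 2223 | 267 | ±0.052 | ±0.038 |
| 30% | 2001 | 240 | ±0.055 | ±0.040 |
| 20% | 1334 | 160 | ±0.067 | ±0.048 |

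For example, at 50% and 12%: 1.96 × √(0.1875 / 400.2) = 0.042.

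At 12%, keeping ±0.03 in a 50% part would need 6670 / 0.5 = 13,340 analysed patients. The recruitment allowance does not close the gap: if all 8004 were analysable, a 50% part (4002 patients, 480 cases) would still give ±0.039.

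**Step 3: optimism from choosing the winner.** The documents do not give the number of models or how alike they are, so this is an illustration only. Suppose K equally good models are compared on sensitivity in a 50% part, with correlation ρ between their errors. The standard error is √(0.1875 / 400) = 0.0217. The expected excess of the best is 0.0217 × √(1 − ρ) × m, where m is the expected maximum of K standard normal values (0.85 for K = 3, 1.54 for K = 10).
- K = 3, ρ = 0.9: 0.0217 × 0.316 × 0.85 = 0.006.
- K = 10, ρ = 0.9: 0.0217 × 0.316 × 1.54 = 0.011.
- K = 10, ρ = 0: 0.0217 × 1.54 = 0.033.

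Models fitted to the same patients with overlapping predictors are highly correlated, so the lower values are the more plausible.

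**Step 4: what the formula promises.** The formula gives the width of an interval if the sensitivity is 0.75. That interval runs from 0.72 to 0.78, so it is not power to show a sensitivity of 0.75 or more.

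**The case against.** The strongest reply has four parts.

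*An independent check is planned.* Section 11 puts external validation before release. This stands. A reader might infer that unbiased validation is lost altogether, and the protocol does not support that. The loss is within the study's own data. The external step has no stated dataset or size, however, so it cannot be credited with ±0.03.

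*The sizes depend on assumptions.* This also stands. The split ratio is unstated, and section 5.1 calls 12% conservative. At 23% a 50% part almost meets the target. A reader might infer that the study needs 13,340 patients, but that holds only for a 50% split at the lowest rate. Moreover, the 12% is the rate of not regaining QoL, whereas section 5.5 models net QoL benefit, for which no rate is given. The case counts may therefore not apply to the model that is built.

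*The selection bias may be small.* Probably so. A reader might infer a serious upward bias in discrimination and calibration, but the documents do not allow any amount to be fixed. Section 11 also mentions the regression and the interaction analysis before the split. One might infer that predictors are screened on the validation patients, but the text does not settle the order.

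*Such details belong in the analysis plan.* This is true of the ratio and of any optimism correction. It does not answer the point, because section 11 states that the validation data are used to choose the model and section 5.1 states a precision that assumes no split. Section 11 names calibration and discrimination and does not say where sensitivity will be estimated. Either answer leaves the conflict: validated but less precise than ±0.03 at the planning rate, or precise but apparent.

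**Conclusion.** The concern holds in a limited form. At the protocol's own 12% planning rate, ±0.03 is not delivered on data independent of model building. The half-width is about ±0.042 to ±0.067 for validation shares of 50% down to 20%, and nearer the target if the case rate is higher (±0.031 for a 50% share at 23%). This rests on section 5.1's inputs, 6670 analysed patients and an assumed split ratio.

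The stated use of the validation data to select the model makes the winner's reported performance optimistic, by an amount that is probably modest and cannot be fixed from the documents. It also leaves no untouched set within the study.

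The size of 6670 is not miscalculated for what its formula describes. It describes something other than the validation in section 11.

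**What to change.** Reconcile sections 5.1 and 11 before the data are analysed, because a validation set once used to choose a model cannot be made untouched again. Two routes work.

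1. **Use all analysed patients for development.** Put every selection step, including interactions, inside bootstrap resampling or internal-external cross-validation by centre. Report optimism-corrected sensitivity together with specificity, c-statistic and calibration. The cost is more computing and no single hold-out set to show.
2. **Keep the split.** State the ratio, choose the model by cross-validation within the development part, and open the validation part once, for the chosen model only. Restate the precision in section 5.1 for the size of that part and for the event rate of the outcome actually modelled. The cost is a less favourable stated precision.

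On either route, replace the claim of power for a minimum sensitivity in section 5.1 with a conditional statement: if sensitivity at the chosen cut-off is 0.75, the 95% interval is ±x, with x taken from the route chosen. Neither route needs more patients or visits.
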